7.4 Sample Size Considerations

The overall sample size was chosen to have up to 18 cisgender women in each relevant group (overall, n=54 non-pregnant cisgender women, 18 pregnant cisgender women) sufficient to provide new information on PrEP use and to balance feasibility, efficiency, and provide robust TDF/FTC data for cisgender women including in pregnancy. The sample size for drug concentration parameters is based on ensuring precision in the estimates to accurately describe the concentration kinetics of TDF/FTC in pregnant and non-pregnant cisgender women and is consistent with multiple DOT PrEP studies done in US populations^{41, 42}. The precision desired is a mean TFV-DP in DBS at steady state within $\pm 15\%$ of the true population mean. The mean (\pm standard deviation) TFV-DP at steady-state in HIV-uninfected US men following directly observed doses of 300 mg TDF/200mg FTC once daily for 12 weeks is 1605 ± 405 fmol/punch [coefficient of variation (CV) of 25.2%] (Anderson *et al*)⁴¹. Based on this variability and assuming average TFV-DP results are normally distributed, to be 90% confident that the DBS TFV-DP sample mean is within 15% ($=60.8$ fmol/punch) of the true mean (concentrations at week 8 of DOT dosing or 1445 fmol/punch which is 90% of steady-state concentration at 12 weeks is 1605 fmol/punch), a sample size of 15 participants is required for non-pregnant cisgender women and, with conservative assumptions, 15 per group for pregnant cisgender women. With planned 18 cisgender women per group for this study, even 10% non-completion rate at 8 weeks of DOT therapy, we will have ample data to estimate steady-state means to within 10% in non-pregnant cisgender women and in pregnant cisgender women.

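### Section 7.4 prints 15% of the standard deviation (60.8) as 15% of the mean, and its 10% precision claim is narrowly missed at about 16 completers per group

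*Combined protocol and SAP*

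**What the plan says.** Section 7.4 states its target in words: "The precision desired is a mean TFV-DP in DBS at steady state within" ±15% of the true population mean. Its only variance input comes from US men on daily observed dosing for 12 weeks: mean 1605, SD and CV given as "405 fmol/punch [coefficient of variation (CV) of 25.2" per cent. It takes the week-8 level as 90% of the 12-week level ("concentrations at week 8 of DOT dosing or 1445 fmol/punch").

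The derivation is normal-theory ("assuming average TFV-DP results are normally distributed") and asks for 90% confidence that "the DBS TFV-DP sample mean is within 15% ($=60.8$ fmol/punch) of the true mean". It concludes that 15 women per group are needed. For the pregnant cohort it also gives 15, on assumptions it calls conservative but does not list.

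The paragraph closes by saying that, with 18 per group and even 10% non-completion, "we will have ample data to estimate steady-state means to within 10% in non-pregnant cisgender women and in pregnant cisgender women".

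**The concern.** The bracketed 60.8 cannot be 15% of either mean in the paragraph: it is 3.8% of 1605 and 4.2% of 1445. A reader who takes it at face value would expect the benchmark mean to be known several times more precisely than the design allows. The closing 10% claim can be checked against the paragraph's own SD and completer count, and it does not come out.

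This is the quantitative part of the sample-size argument in a study whose product is a set of benchmark concentrations. Its stated precision should be reproducible from its stated inputs.

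**Working it through.** **Inputs (all Section 7.4).** SD 405; means 1605 (12 weeks) and 1445 (week 8); CV 405/1605 = 25.2%; confidence 90%, read as two-sided because the target is ±15%; 18 per group less 10% = 16.2, so about 16 completers. The plan does not say whether a normal or a t quantile was used, so both are shown. The 10% sentence gives no confidence level; 90% is carried over from the sentence before it.

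**Formulas.** Half-width h = q × SD / √n, and n = (q × SD / h)², with q = 1.645 (z) or the t quantile on n − 1 degrees of freedom, iterated.

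**1. The printed half-width.**
- 0.15 × 405 = 60.75, which rounds to the printed 60.8.
- 0.15 × 1445 = 216.75.
- 0.15 × 1605 = 240.75.

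**2. The stated n = 15.**

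| Half-width (SD 405) | n by z | n by t |
|---|---|---|
| 60.8 | (1.645 × 405 / 60.8)² = 120.05, so 121 | 122 |
| 216.75 | (1.645 × 405 / 216.75)² = 9.45, so 10 | 12 |
| 240.75 | (1.645 × 405 / 240.75)² = 7.66, so 8 | 10 |

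Fifteen is not reproduced. It, or a value close to it, appears only under settings the plan does not state. With h = 216.75 and SD 405, 95% confidence gives 14 (z) or 16 (t), and 90% confidence with 80% assurance on the interval width gives 15. With 15 women, the chance that the mean falls within 60.8 of the truth is about 44%.

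**3. Is 15 enough for ±15%?** Yes. At n = 15 the 90% half-width is 10.7% (z) or 11.5% (t) with CV 25.2%, and 11.9% or 12.7% with 405/1445.

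**4. The 10% claim at 16 completers.** The quantile t on 15 degrees of freedom is 1.753, and √16 = 4.
- CV 25.2%: 1.645 × 25.2 / 4 = 10.4% (z); 1.753 × 25.2 / 4 = 11.1% (t, using the unrounded CV).
- SD 405 against 1445 (CV 28.0%): 11.5% (z); 12.3% (t), which is 1.753 × 405 / 4 = 177 fmol/punch.
- If instead the CV of 25.2% carries over to week 8, the SD there is about 364, and the t half-width is 1.753 × 364 / 4 = 160 fmol/punch, or 11.0%.

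Every two-sided 90% variant exceeds 10%. Reaching 10% takes 18 (z) or 20 (t) completers at CV 25.2%, and 22 or 24 with 405/1445.

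**5. Pregnant cohort.** The plan gives no CV for pregnant women, so the CVs here are assumptions. With 16 women and t, an assumed CV of 30% gives 1.753 × 30 / 4 = 13%, and 40% gives 18%. The ±15% target is missed once the CV exceeds 15 × 4 / 1.753 = 34%.

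**The case against.** Several points on the other side are sound.

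- **The study is not too small.** A reader might infer from the 121 that each group falls far short. The documents do not support that: the target is stated in words as ±15% of the mean, and 15 to 18 women meet it at the plan's SD. Against that target, 15 is a surplus with unexplained settings.
- **The 10% miss can be very small.** In the most favourable variant it is 10.4%. If all 18 complete, z with CV 25.2% gives 9.8%, although t gives 10.35%. Section 2.5.1 speaks of enrolling until 54 non-pregnant women are evaluable (18 per arm), while Sections 2.6 and 3.8 aim for about 60 evaluable overall (15 per group if spread evenly). The 10% sentence itself allows for 10% loss, so 16 is the fair test.
- **A flat 12% would also be unsupported.** It sets a 12-week SD against a week-8 mean, and the plan gives no week-8 SD. A range is what the inputs allow.
- **The primary model pools the arms.** Section 7.3.1 fits one power model across the three doses. With 16 per arm and a log-scale SD of 0.248, the 90% half-widths for the fitted log means are about 9.7%, 6.0% and 9.3% at 2, 4 and 7 doses. This depends on the model holding and leaves out the pregnant cohort, and Section 7.4 does not invoke it. It does mean that 10–12% must be labelled as a single-group figure.
- **The calculation is not the sole basis for the group size.** Section 7.4 also cites feasibility, efficiency and consistency with earlier US studies of observed dosing.

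A reader might also infer that the precision promised for the 25th-percentile thresholds is wrong. Section 7.4 promises none, so there is no stated figure to correct.

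**Conclusion.** Two figures in Section 7.4 are wrong as written. The 60.8 is 15% of the SD; the matching value is 217 fmol/punch (of 1445) or 241 (of 1605). The 10% precision is not reached for a single-group mean at about 16 completers, where the two-sided 90% half-width is about 10–12%. In addition, 15 per group cannot be reproduced at the stated confidence.

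The conclusion on 60.8 is plain arithmetic. The conclusion on 10% assumes two-sided 90% confidence, 16 completers, one group analysed on its own, and a CV of 25–28% taken from US men. A larger CV, which the plan does not rule out for pregnant women, would widen it. The consequence is a modest overstatement of precision; it affects neither the adequacy of the sample for ±15% nor any planned analysis.

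**What to change.** In Section 7.4:

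1. Replace 60.8 with 217 fmol/punch, identified as 15% of the week-8 mean of 1445.
2. Correct the derivation, and give the formula and settings behind 15 (z or t, confidence level, any assurance on interval width). Alternatively, say that about 8–12 suffice and that 15 leaves a margin.
3. Replace the 10% claim with wording such as: *within about 10–12% (two-sided 90% CI for a single-group mean, 16 evaluable per group, assuming a CV of 25–28%)*.
4. For the pregnant cohort, say that the figure assumes the CV seen in US men and would widen with a larger one: about 13% at an assumed CV of 30%, about 18% at 40%, with the 15% target missed above about 34%.

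The cost is a few sentences and a slightly less favourable stated precision. Enrolment and analysis are unchanged.

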7.5 Randomization and Blinding Procedures

The study design for non-pregnant cohort will be an open-label, randomized study with three arms. The randomization assignments cohort will be made at enrollment if the participant is eligible and agrees to enroll. Randomization will be according to the PrEP dosing frequency and vaginal tissue collection plan (either sampling day 4 or day 7) 1:1:1 fashion programmed by the study statistician and generated from REDcap. Randomization will be done at enrollment.

The allocation of participants for the 3 study arms will be the following:

	2 doses per week	4 doses per week	7 doses per week	Total
Total	18	18	18	54

The study design for the pregnant cohort will be an open-label, non-randomized study with only DOT PrEP daily dosing regimen (7 doses per week).

7.6 Planned Interim Analyses

Because the study is non-therapeutic and relatively small ($N < 100$) the study team will monitor for safety as described above, but not efficacy. Thus, drug concentration outcomes will not be part of the assessment as samples will be batched tested at the end of the primary data collection. At least one Formal Interim Analysis at 50% enrollment (overall or 50% recruitment for pregnant cohort, whichever occurs first) to review data related to patient safety, including baseline characteristics, creatinine

clearance, HIV infections, and pregnancy outcomes (preterm birth, pregnancy loss, birth defects). The study team will carefully document any adverse events in pregnant cisgender women or infants for careful review.

8 HUMAN SUBJECTS CONSIDERATIONS

8.1 Ethical Review

This protocol and the template informed consent form contained in Appendix and any subsequent modifications — will be reviewed and approved by the DAIDS Prevention Science Review Committee with respect to scientific content and compliance with applicable research and human subjects' regulations.

The protocol, site-specific informed consent form, participant education and recruitment materials, and other requested documents — and any subsequent modifications — also will be reviewed and approved by the University of Washington Human Subjects Ethical Committee and the Scientific and Ethics Review (SERU) Committee of the Kenya Medical Research Institute responsible for oversight of research conducted at the study site.

Subsequent to initial review and approval, the responsible IRBs/ECs will review the protocol at least annually. The Investigator will make safety and progress reports to the IRBs/ECs at least annually, and within three months of study termination or completion. These reports will include the total number of participants enrolled in the study, the number of participants who completed the study, all changes in the research activity, and all unanticipated problems involving risks to human subjects or others. The study site is responsible for the submission of continuing review to the DAIDS Protocol Registration Office, in accordance with the current DAIDS Protocol Registration Policy and Procedure Manual.

8.2 Informed Consent

In obtaining and documenting informed consent, the investigators will comply with all applicable local and/or domestic regulatory requirements and will adhere to Good Clinical Practices and to all ethical principles from the Declaration of Helsinki. A trained research staff person will conduct the informed consent process. Written informed consent will be obtained individually from each participant. Staff will explain the study, read the consent form, and answer any questions the participant may have. Consent information will describe the purpose of the study, the procedures to be followed, and the risks and benefits of participation, in accordance with all applicable regulations. We will translate the forms into the local language (Kiswahili) and verify the accuracy of the translation by performing an independent back-translation. The consent process will occur either in English or the local language (Kiswahili) depending on the participant's preference. We will perform paper-based and/or electronic-based consenting of participants. For the electronic version, we will program the complete consent form with signature pages onto tablets and participants will read along on the tablet during the consenting process. The study team member conducting consent will allow the participant time to ask any questions that they may have before signing the consent form. After we have ensured that participants have read and understood the consent forms, we will ask them to append their signature on the tablet. The signature will be stored electronically. In addition, any participant who wants their consent form to take home will have a paper copy printed and given to them. At each visit after enrollment, participants will have the opportunity to ask questions and the study staff will remind them their participation is voluntary. Participants will be informed that they may withdraw from any of the research procedures at any time, without it affecting the care they receive at the clinic

8.3 Voluntary Participation

The consenting process will emphasize and give information that study participation is voluntary and that the participant can withdraw from the study at any time without losing the care they would otherwise receive.

8.4 Potential Risks to Human Subjects

Safety assessment will be measured in all participants: serious adverse events (SAEs), related Grade 3 and 4 AEs and discontinuations, and a side effects. The medical risks of blood collection and vaginal tissue collection are small, with some anticipated mild discomfort from vaginal speculum insertion, and venipuncture. Participants may become embarrassed, worried, or anxious while undergoing pelvic exams for collection of samples.

Risks related to non-daily PrEP dosing

Participants will be randomized to one of 3 directly observed dosing patterns: 2, 4 or 7 TDF/FTC doses per week. Only daily PrEP is recommended by WHO and the Kenya national guidelines for protection from vaginal HIV exposure and we have carefully considered the risks associated with non-daily in planning this proposal. We have carefully considered the risk associated with using non-daily dosing for PrEP (i.e., 2 or 4 doses per week) in non-pregnant cisgender women and the potential for risk of HIV infection for those non-daily dosing. The non-daily dosing is needed to help investigate and demonstrate dose proportionality of TFV and TDF-DP concentrations. The adherence-concentration thresholds derived from this dosing frequency will be important to estimate efficacy levels derived from varying adherence patterns, including suboptimal dosing. As detailed in [eligibility section](#), only cisgender women at low risk of HIV based on Kenya guidelines will be enrolled and cisgender women will receive full package of HIV prevention, including risk reduction counseling, condoms and STI treatment at each visit. We will also perform monthly HIV testing. We will use Kenya national guidelines to guide identification of cisgender women at elevated risk of HIV to guide recruitment into this study. Each visit will include risk-reduction counseling for all cisgender women. All participants in this study will have HIV test at baseline and then every 4 weeks and PrEP will be immediately discontinued in case of seroconversion.

Risks related to TDF/FTC PrEP

Study medication risks and side effects related to PrEP include: occurring in a minority of individuals taking PrEP - gastrointestinal intolerance, such as nausea, diarrhea or vomiting, flatulence typically during the first month after PrEP initiation; rare but serious side effects of lactic acidosis/ severe hepatomegaly with steatosis, renal impairment, including cases of acute renal failure and Fanconi's syndrome (renal tubular injury with severe hypophosphatemia), increase in bone metabolism leading to osteopenia, and hypersensitivity reaction. The risks of side effects of antiretroviral treatment (ART) are similar to those of PrEP and also rare but serious complications such as lactic acidosis.

Risks from vaginal biopsy

Vaginal tissue biopsy is an invasive procedure and we have carefully considered the risk involved including some discomfort, pain and potential for bleeding and burden on cisgender women. Sampling vaginal tissue is important to fully characterize HIV protection in cisgender women since it is the tissue of relevance to the acquisition of HIV infection for cisgender women and will help to define early drug kinetics and how soon drugs accumulate in vaginal tissue from PrEP initiation until steady state. To minimize risks, we have carefully considered sampling schedule. We have carefully considered our sampling schedule to minimize risk associated with this procedure and burden on cisgender women: 1) Only non-pregnant cisgender women will provide samples 2) Each woman will provide only one biopsy in a 4-week period by sampling unique cisgender women (i.e. for each planned tissue sampling visits (i.e., separate cisgender women each at day 4, Week 1, 4, and 8).

Social harm and stigma risks

We have considered the risk of social harm related to both DOT PrEP use and frequent clinic visits, including risks of depression/anxiety and disclosure and stigma. Our extensive experience with successful and safe longitudinal follow-up of cisgender women at risk mitigates some of this risk, and we will measure social harms and provide/refer for services when harms are reported. Participants also may become embarrassed, worried, or anxious while completing surveys or interviews regarding sexual behavior and acceptability. Counseling will be provided by clinical study staff who have been trained in specific issues related to STI/HIV risk, PrEP, STI/HIV acquisition, and care of HIV infected cisgender women, including stigma, blame, methods to avoid transmission, and available support services.

Behavior disinhibition risks

The potential for behavior disinhibition may exist as a result of PrEP and is an important outcome, especially given the potential for some participant to receive less than daily dosing of PrEP. We will use brief standardized questionnaires, which we have used for prior studies in cisgender women to explore partner number, sexual frequency, and condom use over time.

Risks of TDF/FTC PrEP use in Pregnancy

There may be risks when taking any drug in pregnancy including for TDF/FTC PrEP. However, PrEP is safe for use in pregnant cisgender women and approved in Kenya as one option for protection against HIV acquisition. TDF and FTC have been used for a long time for treatment in HIV-uninfected pregnant cisgender women and there is no current evidence that PrEP harms babies of women who use it during pregnancy, but it recognized that additional data is needed still helpful to verify this. Pregnancy is associated with gastro-intestinal symptoms (e.g., nausea, vomiting) which are similar to PrEP-related symptoms and therefore use of PrEP in pregnancy could potentially exacerbate these symptoms.

Risk of related to vaginal swabs in pregnancy

Although there is a theoretical possibility of risk of performing vaginal swabs in pregnancy (e.g., precipitating labor), the likelihood of happening is very low with cotton swabs planned for this study and we take confidence from the experience with studies involving pregnant cisgender women at Thika site with similar procedures (Table 4 in the protocol). Importantly, these risks will be discussed with the participants and they will be asked to inform the clinical research team if any of these occur. If a patient develops serious side effects from the medication, then they will be asked to stop the study.

Privacy and confidentiality risks

Although study site will make every effort to protect participant privacy and confidentiality, it is possible that participants' involvement in the study could become known to others. For example, participants could be treated unfairly or discriminated against, or could have problems being accepted by their families and/or communities. We have extensive experience with the strategies to minimize the potential for social harms in populations participating in HIV prevention studies.

Risks from other study procedures

Blood for safety labs and study pharmacological samples will be collected from each subject during the study period. Blood will be collected from an arm vein and by fingerstick. Risks of blood draws include pain when the needle or lancet pierces the skin, bruising, and/or infection. The blood volumes are well below the maximal volumes set for blood donations and clinical research in 9 weeks. Approximately 100 strands of hair will be cut from the occipital portion of the scalp on multiple occasions. This could leave a noticeable spot where the hair was cut from.

8.5 Approaches to Minimize Risks

Protection of risks related to non-daily PrEP dosing

We have carefully considered the risk associated with using non-daily dosing for PrEP (i.e., 2 or 4 doses per week) in non-pregnant cisgender women and the potential for behavior disinhibition as a result of PrEP is an important outcome. We will make all effort to enroll only healthy cisgender women volunteers deemed at low risk for HIV. We will use Kenya national guidelines as well as published HIV risk score (Voice risk) to guide identify cisgender women who may be at elevated risk of HIV to guide recruitment into this study—those found to at elevated risk for HIV will be immediately linked for PrEP and other prevention services here at the Thika site or at the participants' clinic of choice. Each visit will include risk-reduction counseling for all cisgender women. All participants in this study will have HIV test at baseline and then every 4 weeks and PrEP will be immediately discontinued in case of HIV seroconversion. Non-pregnant cisgender women identified to be at elevated risk of acquiring HIV through screening will be immediately linked for PrEP at study clinic site itself or at participant's clinic of choice.

Protection against risks related to TDF/FTC PrEP

All participants will have HIV testing, creatinine testing, hepatitis B, and urine pregnancy testing at baseline. Only cisgender women with creatinine clearance >60 mL/min and uninfected with hepatitis B will be enrolled. We are testing volunteers for HBV-infection to protect subjects from HBV-associated hepatitis flares when the drugs are withdrawn. Breastfeeding will not be allowed to prevent risks to nursing infants. We are excluding subjects who have serious underlying illnesses such as cancer and heart disease. All clients will be counseled about potential side effects at enrollment and each follow up visit and they will be reminded that the side effects are self-limiting within 1-2 weeks. Subjects will be followed with clinical laboratories at entry and 8 weeks (serum creatinine, complete hematology, monthly pregnancy urine test) and more frequently with interviews to assess tolerability and safety over the course of the study, including during directly observed dosing. Participants will be tested for HIV infection at any point during the study as needed, and prior to and at the final visits of the dosing periods.

In summary, the most likely risks associated with TDF-FTC in HIV-negative persons appear to be reversible gastrointestinal complaints, headache, and/or weight decrease. These side effects are most likely mild and reversible.⁷⁹ There is a remote risk of serious or fatal side effects including renal failure, lactic acidosis with hepatomegaly and steatosis, bone pathology, hypophosphatemia, hepatitis, pancreatitis, and there are possible side effects not listed here, or possible unforeseen long-term complications. We believe the risk of these serious side effects is remote given the rarity of the events during long-term treatment and PrEP in previous studies. We have designed the inclusion and exclusion criteria to exclude subjects who might be at higher risk of these toxicities. We have also designed a monitoring strategy for early detection of side effects and for quick study drug discontinuation, if needed, to protect subjects.

Protection of risk related to vaginal tissue biopsy

We have also carefully considered our sampling schedule to minimize risk associated with vaginal tissue biopsy and burden on cisgender women and will take the following measures: 1) Only low HIV risk non-pregnant cisgender women will provide vaginal tissue samples 2) Each woman will provide only one biopsy in a 4-week period by sampling separate cisgender women during the first week (i.e. ~half on day 1 and the other half on day 7, ensuring sufficient time before week 4 sample. All non-pregnant cisgender women will provide week 4 and 8. Cisgender women will be counseled to avoid sex in ~7 days after biopsy.

Protection against risks in pregnancy

To ensure an ethical approach for provision of PrEP in pregnancy (i.e., only exposing PrEP to those who

want and might benefit from it), all pregnant cisgender women will be at high risk for HIV and will receive only daily PrEP dosing (7 doses per week). HIV risk and eligibility will be determined according to the Kenya guidelines for PrEP. Pregnant cisgender women will receive only daily PrEP dosing (7 doses per week). After 8 weeks of DOT PrEP, pregnant cisgender women will be linked to continue PrEP at the clinic of their choice, including at the Thika site clinic itself, permitting seamless access to PrEP and continuation after the study. For the initially non-pregnant cisgender women, if they become pregnant, study drug will be discontinued unless they have an indication for PrEP for which daily dosing will be provided. Cisgender women will be followed to obtain pregnancy outcomes until end of study.

Reducing social harm risks

In addition to protecting the privacy of participants, as described above, we will monitor for social harms. Social harms will be recorded on separate case report forms. Severe unexpected social harms will be considered unexpected problems and reported to the IRB according to local regulations. Social harms will be included on summary reports for the PSRT, as described in this protocol.

Reducing risks behavior disinhibition

We will use brief standardized questionnaires, which we have used for prior studies in cisgender women to explore partner number, sexual frequency, and condom use over time. Each visit will include risk-reduction counseling for all cisgender women and cisgender women will be provided with condoms. Importantly, only cisgender women at low risk of HIV will be enrolled in the non-pregnant cohort which has potential for assignment for non-daily dosing.

Reducing risks from other study procedures

The blood will be collected from an arm vein, and/or by finger stick, by trained staff at the study site according to standard medical procedures. Hematology will be monitored. The hair that is cut will be taken from underneath the top layer of hair to minimize the ability to see where the hair was cut from and to avoid sun-bleached hair.

All participants in this study will have HIV test at baseline and then every 4 weeks. All data received at the University of Washington will be labeled only with participant ID number and no identifying information will be transmitted. The study team has extensive experience with counseling about HIV risk, PrEP (and ART), and strategies for HIV prevention in general. In addition to PrEP and STI treatments, condoms will be provided to all participants by the study site and will follow Kenya clinical guidelines. Counseling about safe sex and medication adherence for prevention will include messaging describing the benefits of all strategies, based on evolving available data and national policies for HIV prevention.

For data collection, standardized questionnaires will be used that will include questions on sensitive topics, including sexual behavior, and stigma. We have extensive experience with these questionnaires from our prior studies and the expertise and counseling resources required to attend to study participants. We have extensive experience with management of potential social harms, through our prevention studies. The risks from the anticipated activities will be no greater than in our previous studies; in fact, given the proven prevention benefits of PrEP and now normalized national roll-out in Kenya, risks are anticipated to be less than in some of our prior studies.

8.6 Benefits.

Participants will benefit from ongoing access to PrEP as now part of standard clinical care. However, the participants or others may benefit in the future from information learned in this study, including contribution to the understanding about HIV prevention and effective PrEP use in cisgender women in Africa, which will help others in the future. While enrolled in the study participants will get access to all services available to those not in the study such as access to oral PrEP (which is known to help prevent

HIV infection), counseling for reducing risk of getting HIV from their sexual partner, and provision of free condoms. For care and treatment that is not available at the clinic, study staff will inform and refer participants to other health facilities where care and treatment may be available.

